#### 5.2.2 – Exclusion criteria

Patients who meet any of the following criteria will be excluded from the investigation:

1. Paroxysmal and short-standing AF  $<$  3 months
2. Long-standing persistent AF  $>$  5 years ( $\geq$  1 year in the United States)
3.  $\geq$  2 previous ineffective cardioversion sessions in case of undetermined AF duration
4. Severe obesity (BMI  $>$  40)
5. Very dilated Left Atrium (LA) (e.g. LA diameter  $>$  60 mm and/or LA surface  $>$  40 cm^2 determined by 2D echocardiography)
6. Patients with AF secondary to an obvious reversible cause
7. Inadequate anticoagulation as defined in the inclusion criteria
8. LA thrombus on Transesophageal Echocardiography (TEE)\* or CT Scan prior to procedure
9. Contraindications to anticoagulation (heparin, warfarin or NOAC)
10. Patients who are or may potentially be pregnant
11. Previous surgical or catheter ablation for AF
12. Any cardiac surgery within the past 2 months (60 days) (includes PCI)
13. Myocardial infarction within the past 2 months (60 days)
14. Previous AV valve surgery
15. History of blood clotting or bleeding abnormalities
16. Documented arterial thromboembolic event (including TIA) within the past 12 months (365 days)
17. Rheumatic Heart Disease
18. Chronic severe Heart Failure (NYHA functional class IV and/or LVEF  $<$  25%)
19. Awaiting cardiac transplantation or other cardiac surgery within the next 12 months (365 days)
20. Unstable angina within the past month
21. Acute illness or active systemic infection or sepsis
22. AF secondary to electrolyte imbalance, thyroid disease, or reversible or non-cardiac cause
23. Diagnosed atrial myxoma
24. Significant severe pulmonary disease (e.g. patients with restrictive pulmonary disease, constrictive or chronic obstructive pulmonary disease in GOLD stage IV) or any other disease or malfunction of the lungs or respiratory system that produces chronic symptoms (e.g. unstable or untreated sleep apnea)

 An effective cardioversion means that normal sinus rhythm has been restored at the end of the procedure and that the last ECG before discharge shows a sustained sinus rhythm.

 An ineffective cardioversion means that normal sinus rhythm could not be restored at the end of the procedure or that the last ECG before discharge indicates a reversion to AF.

 <small>ARTIFICIAL INTELLIGENCE SERVING HUMANITY BETTER</small>	CLIPL-01-002-E	CONFIDENTIAL
	CLINICAL INVESTIGATION PLAN	F 09 XX 01 Rev.A

25. Significant congenital anomaly or medical problem that in the opinion of the investigator would preclude enrollment

26. Enrollment in an investigational study evaluating another device, biologic, or drug

27. Presence of intramural thrombus, tumor or other abnormality or condition that precludes vascular access, or manipulation of the catheter

28. Life expectancy or other disease processes likely to limit survival to less than 12 months

29. Acute Covid-19 infection (fever and/or biological inflammatory syndrome, and positive test documented)

\*Only TEE is acceptable in the United States to screen for LA thrombus. If a subject cannot have a TEE performed, then intracardiac echocardiography at the beginning of the procedure to screen for LA thrombus is acceptable.

#### 5.2.3 – Criteria and procedures for withdrawal or termination of a subject's participation

A patient's participation ends if any of the following occurs:

- At the end of 12-month follow-up period or if relevant, after resolution of a study-device-related adverse event ongoing at the time of the 12-month follow-up
- If the patient does not undergo an AF catheter ablation
- At any time, in the event of withdrawal of consent or cooperation by the patient
- At any time, if the patient is lost to follow-up
- At any time, in the event of patient's exclusion from the study, required for safety reasons according to the investigator's judgement
- In the event of the patient's death
- At any time, in the event of withdrawal of approval from relevant Ethics Committee or IRB

In each of the above termination cases, the appropriate case report form must be completed to document and justify the end of a patient's participation in the study.

If an adverse effect due to the implementation of the protocol is observed, the study may be suspended at any time by the sponsor.

Premature termination of the study may occur motivated by a general decision (Ethics Committees, IRBs, regulatory Competent Authorities, Data Safety Monitoring Board) for safety reasons related to the use of the device or study procedures.

A site may be terminated for the following reasons: failure to comply with the conditions of the study protocol and/or failure to accurately complete case report forms.

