### 5.3.8 – Blanking periods

After the index procedure, a 6-week absolute blanking period will be applied, during which a repeat procedure is not allowed, only cardioversions are allowed if necessary.

After this absolute blanking period and before the end of the standard 3-month blanking period, a repeat procedure is discouraged but not prohibited. The decision to perform a repeat procedure before the end of the 3-month blanking period is left to the operator's discretion. If a repeat procedure is performed during the 3-month blanking period, the recurrence and the repeat procedure are counted as occurring at 3 months.

After a repeat procedure, a 2-week blanking period will be applied, during which AF/AT recurrences will not be counted. Any re-repeat procedures will be performed outside the study according to the operator's preferred approach and will result in the data being censored at the time of the re-repeat procedure. The patient will however stay in the study for safety purposes.

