## **VI – STATISTICAL CONSIDERATIONS**

### **6.1 – Design, statistical methodology and analytical procedures**

Standard summary statistics will be calculated for all study variables (demographics and outcomes) by study group and for all patients. For continuous variables, statistics will include means, standard deviation and 95% confidence intervals for means when assumptions of normal distribution are not violated. Median and quartiles may also be presented. Categorical variables will be summarized using frequency distributions.

The analysis for the primary endpoint will be a modified Intention-To-Treat (mITT) analysis, allowing exclusion of some randomized subjects in a justified way:

- Patients that are deemed ineligible after randomization or that do not have any AF ablation will be excluded
- Patients in the Tailored group for whom AF cannot be induced and who undergo conventional ablation will be included in this analysis
- Patients lost to follow-up (death, disability, relocation, or drop-out) during the 3-month blanking period will be excluded
- Patients who complete at least their 3-month follow-up but who are lost to follow-up (death, disability, relocation, or drop-out) before the 12-month follow-up will be included in the analysis and the data will be censored
- Patients who undergo a 3rd ablation procedure (re-repeat procedure) will be included in the analysis but the data will be censored at the time of the 3rd procedure.

A per-protocol (PP) population will also be evaluated and will serve as supportive analyses to the mITT analysis. In the PP analysis, the population will be analyzed according to the treatment actually received at the start of the study, and will consist of patients that met all the inclusion criteria, none of the exclusion criteria, were successfully treated, had no important protocol deviations and attended all the scheduled follow-up visits.

 <small>ARTIFICIAL INTELLIGENCE SERVING HEART DISEASE</small>	CLIPL-01-002-E	CONFIDENTIAL
	CLINICAL INVESTIGATION PLAN	F 09 XX 01 Rev.A Page 33/47

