#### 6.7 – Missing data and sensitivity analysis

Subjects who miss a study visit should be contacted immediately by the Investigational site to determine the reason for the missed visit and to reschedule the visit as soon as possible to meet the study visit window. If the subject cannot be located after 3 attempts by phone, email and/or letter, then the subject will be considered lost to follow-up. All attempts to contact the subjects will be documented and retained in the subject study record.

With regard to the main judgement criteria, data will be censored if the patient is lost to follow-up (death, disability, relocation, or drop-out).

As the burden of study participation does not differ between the tailored and the anatomical arm, we expect all study losses to be non-differential with respect to treatment assignment. Thus, our results will not be biased as a result of these losses.

Additional supportive analyses will be performed on the primary endpoint to assess the effect of missing data.

For missing demographic data, the data will not be replaced because it has no weight on the main judgment criterion.

A rigorous monitoring is expected, any missing data will be filled in during these visits.

	CLIPL-01-002-E	CONFIDENTIAL
	CLINICAL INVESTIGATION PLAN	F 09 XX 01 Rev.A Page 35/47

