4.3.1 Secondary Analysis

The secondary endpoint analyses will consist of the following:

Two tests of the primary endpoint in the mITT population, but expanded to be defined as freedom from AF/AT, with or without AADs, 12 months after one or two procedures. A superiority hypothesis will be tested using a Cox proportional hazards model with randomization group, AF duration, and AF/AT strata as fixed effects, with a one-sided alpha level of 0.025:

Both analyses under will be evaluated according to the following hypotheses:

$$H_0$$
: $S_1(t) = S_2(t)$

$$H_A$$
: $S_1(t) > S_2(t)$,

where $S_1(t)$ and $S_2(t)$ represent the survival functions for the Tailored and Anatomical arms, respectively, at any given time t. If the null hypotheses for each of the tests is rejected, the following superiority statements will be considered on behalf of each endpoint:

- 1. Tailored ablation is superior to anatomical with respect to freedom from AF/AT, with or without AADs, 12 months after one or two procedures.
- 2. Tailored ablation is superior to anatomical with respect to freedom from AF/AT, with or without AADs, 12 months after one procedure.

Similarly to the primary endpoint analyses, Cox Proportional hazards regression models will be fit and assessed for goodness-of-fit. Then to test each null hypothesis, one-sided Log-Rank Tests will be. Just like under the primary analysis, the p-value from the one-sided Log-Rank Test run under each Cox Proportional hazards model will ultimately be what is used to either reject (p < 0.025) or fail to reject ($p \ge 0.025$) the null hypotheses above. Both Cox models will be conducted in the mITT population.

Kaplan-Meier plots will be generated for each endpoint, to visually display the differences among the survival distributions of the Tailored and Anatomical arms, respectively, with each plot accommodated by the p-value generated from their respective one-sided Log-Rank test.

3. The composite adverse event (AE) rate defined as the number of AEs per month occurring in each treatment arm from time of index procedure through to 12-month follow-up, where composite AEs are defined by either death, a cerebrovascular event, or any serious procedure-related adverse event, will be conducted. in the Safety population (see Section 4.5, Safety Endpoints below).

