4.5 SAFETY ENDPOINTS

The safety endpoint is a composite endpoint at 12 months of the following: death, cerebrovascular events, or serious treatment-related adverse event. Because the rates of this endpoint which are observed under each of the study arms may or may not prove to be relatively rare (< 5% within a given arm), two methods of analysis are provided, the one which will ultimately be used to analyze the safety endpoint will depend on its rate of occurrence, as observed across the two study groups. The safety endpoint analysis, regardless of the method employed, will be conducted in the Safety population. The same analysis will also be conducted in the mITT and PP populations, since if rare occurrence of the safety endpoint is observed and the few occurrences observed happen to all occur within the mITT/PP populations, then the smaller subject sample sizes will serve to increase the rates/proportions observed in each study arm.

METHOD 1 (safety endpoint occurrence > 5% in each study arm):

The safety analysis will be to compare the AE composite rate per month (defined as the 4th secondary endpoint in Section 1 Protocol Summary) under the Tailored (treatment) arm against the Anatomical (control) arm AE composite rate per month from the time of index procedure until the 12-month follow-up. A two-sided 95% CI will be generated for the rate ratio (λ_t/λ_c) comparing the AE composite rate for the two study arms.

Let λ_c and λ_t denote the rate of composite adverse events for the Anatomical and the Tailored treatment arms, respectively. Given a non-inferiority margin δ , the null and alternative hypotheses are:

$$H_0: \frac{\lambda_t}{\lambda_c} \ge 1 + \delta$$

$$H_1: \frac{\lambda_t}{\lambda_c} < 1 + \delta$$

 λ_t,λ_c , and $\frac{\lambda_t}{\lambda_c}$ will be estimated with a linear fixed effects model with a log link function and a Poisson distribution for the number of adverse events (referring only to those defined under the composite AE endpoint). The outcome of the model is the number of composite AEs for each subject enrolled and randomized to one of the study arms. The model will

include an indicator variable for Study Arm, an offset for the log of the number of weeks each subject remained enrolled in the study will be added (the date of each subject's index procedure will be regarded as their first day on the study). In the event the model fails to converge, it will be refit with a Negative Binomial distribution.

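### An investigator's safety exclusion after ablation ends all data collection, so later safety events and the rhythm outcome of those patients are lost

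*Protocol*

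**What the plan says.** Protocol 5.2.3 begins "A patient's participation ends if any of the following occurs", and one entry reads "At any time, in the event of patient's exclusion from the study, required for safety reasons according to the investigator's judgement". Section 5.2.5 refers back to the same list. The site's only stated duty is to complete a form that documents and justifies the exit. The single extension of follow-up in 5.2.3 runs until "after resolution of a study-device-related adverse event ongoing at the time of the 12-month follow-up", so it does not reach a patient who left before month 12.

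Protocol 5.3.8 takes another route for a third ablation. Data are censored at that procedure, but "The patient will however stay in the study for safety purposes". Neither document has a matching sentence for safety exclusions.

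On analysis:

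- **Safety.** SAP 4.3.1 counts composite events "occurring in each treatment arm from time of index procedure through to 12-month follow-up", in everyone randomized and ablated (SAP 4.1.1). Under Method 1 in SAP 4.5, "an offset for the log of the number of weeks each subject remained enrolled in the study will be added". Method 2 compares proportions of all subjects against a 2.5-point margin. SAP 4.5.1 plans no imputation for adverse events.
- **Rhythm.** Protocol 6.1 states: "Patients lost to follow-up (death, disability, relocation, or drop-out) during the 3-month blanking period will be excluded". SAP 4.1.2 also removes losses during blanking. Later losses are censored (Protocol 6.1 and 6.7; SAP 4.2.3 and 6.3).
- **Assumption.** Protocol 6.7 and SAP 6.3 argue that both arms carry the same participation burden, that losses will therefore be unrelated to arm, and that no bias follows.

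**The concern.** After the index ablation, most of what remains in the protocol is observation: visits, ECGs, Holter, weekly telephonic recordings and adverse-event review. Ending participation for a safety reason stops that observation in patients who have just given a reason to be watched.

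Two results are exposed. The 12-month safety composite cannot include events that happen after exit. The primary comparison loses the patient's AF outcome for a reason that may be linked to the procedure.

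The equal-burden argument does not cover this kind of exit. Protocol 5.1.1 blinds only the patient, so the investigator who decides can know the arm. Protocol 7.3 expects more RF time, more ablated area and slightly longer procedures in the Tailored arm.

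**Working it through.** **1. The plan's own figures.** From Protocol 6.2: freedom from AF 62% and 77%, one-sided alpha 0.025, power 80%.

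- HR = ln(0.77)/ln(0.62) = 0.547, as stated.
- Schoenfeld events: 4 × (1.960 + 0.842)² / (ln 0.547)² = 86.3, so 87. Mean event probability (0.38 + 0.23)/2 = 0.305. 87/0.305 = 285.2, so 286 patients, close to 292.
- A Lakatos-type log-rank calculation with exponential curves gives 80.0% power at 292.
- 292/0.78 = 374.4, against the stated 374.

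The sample size is not in dispute.

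**2. How a safety exclusion would be analysed.** Protocol 6.1 and 6.7 list death, disability, relocation and drop-out as loss to follow-up. Protocol 6.7 and SAP 6.3 also apply the term to a patient who cannot be located after three attempts. A safety exclusion is in neither description. If it is read as drop-out, an exit during blanking leaves the mITT set and a later exit is censored.

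**3. Loss unrelated to outcome.** Losing a further 1%, 2% or 5% of the 292 gives power of about 79.6%, 79.2% or 78.0%. Precision is a minor matter.

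**4. Loss related to outcome.** Assume no true effect (38% recurrence in both arms, 146 per arm) and exclusions in the Tailored arm only. Let f be the fraction excluded and R their recurrence risk, with none of their recurrences seen.

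- Apparent Tailored recurrence: p = (0.38 − fR)/(1 − f)
- Apparent HR = ln(1 − p)/ln(0.62)
- Shift in the test statistic = −ln(HR) × √(d q(1 − q)), where d is the number of observed events and q the Tailored share of patients
- One-sided alpha = 1 − Φ(1.960 − shift)

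Example with f = 5%, R = 100%: p = 0.33/0.95 = 0.347 and HR = 0.893. d = 138.7 × 0.347 + 146 × 0.38 = 103.7 and q = 0.487. The shift is about 0.58, so alpha is about 0.083.

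| Excluded, Tailored only | R = 38% | R = 60% | R = 80% | R = 100% |
|---|---|---|---|---|
| 1% | 0.025 | 0.027 | 0.030 | 0.032 |
| 2% (about 3 patients) | 0.025 | 0.030 | 0.035 | 0.041 |
| 5% (about 7 patients) | 0.025 | 0.040 | 0.058 | 0.083 |

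Under the planned effect, 5% excluded with R of 50–100% would lift apparent Tailored freedom from AF from 77.0% to 78.4–81.1%: (0.23 − 0.025)/0.95 = 0.216 and (0.23 − 0.05)/0.95 = 0.189 recurrence.

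**5. Safety Method 2.** Excluded patients stay in the denominator and their later events are unseen. The understatement is f × r, where r is the later composite risk (assumed).

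- f = 2%, r = 10–25%: 0.2–0.5 points, or 8–20% of the 2.5-point margin.
- f = 5%, r = 10–25%: 0.5–1.25 points, or 20–50% of the margin.
- One unseen event in 187 patients is 0.53 points.

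**The case against.** The best defence is that the rule will seldom be used after ablation. Little of what remains is hazardous, so an investigator would rarely judge exclusion necessary. Some exclusions will fall in the 0–90 days between enrollment and ablation, where this point does not arise. Protocol 7.2 expects no added adverse effects from the device, and 7.3 describes RF time, area and duration as within industry norms. Both documents promise supportive analyses for missing data, and the removed consent pages may deal with data collection after exit. All of this limits the likely size. It does not supply the missing rule: the supportive analyses are not described, and the one sensitivity analysis specified for the primary endpoint (per-protocol, SAP 4.2.4) requires attendance at follow-up, so it cannot recover these outcomes.

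Three stronger readings are tempting, and the documents do not support them.

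- **That all 12-month safety information on these patients is lost.** Serious events are reportable within 24 hours, with a resolution date where applicable (Protocol 14.2). The patient remains in the Safety population, so the event that prompted exclusion can count.
- **That after ablation there is no study procedure left to stop.** Protocol 5.3.7 provides for one redo between months 3 and 9 with arm-specific methods, so the rule can have a function after the index procedure.
- **That shorter time enrolled by itself distorts the Method 1 rate ratio.** The log-weeks offset corrects for shorter exposure under a constant event rate. A shift from lost person-time appears only if the excluded patients would have had no later events, the opposite of the worry here. SAP 4.5 also concedes that the test is under-powered. With equal rates and about 10 events per arm (5% of 187 is 9.4), the upper 95% limit is about exp(1.96 × √0.2) = 2.4, against a margin of 1.05. The direction of any Method 1 bias is uncertain.

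**Conclusion.** The point holds in a limited form. As written, the protocol ends observation of an ablated patient whom the investigator excludes for safety, and no visible text in either document continues it. The losses are later composite events, remaining exposure and the rhythm outcome. How the analysis treats these patients has to be inferred.

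The size is unknown because no exclusion rate or risk is given. It is negligible near 1% excluded, or if excluded patients carry average risk. At an assumed 2–5% excluded in the Tailored arm only, with 60–100% recurrence risk and no true effect, one-sided alpha is about 0.03–0.08. Under Method 2, a 10–25% unseen later risk hides about 0.2–1.25 points of the 2.5-point margin. These figures are one-sided by construction. Exits concentrated in the Anatomical arm would push the other way, and balanced exits would largely cancel. That excluded patients are at higher risk is a fair inference from the stated reason for exclusion, but it is not a finding. A reader should not conclude that the trial is biased towards Tailored ablation. The supportable conclusion is that the assurance of arm-independent losses does not cover this route of exit.

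**What to change.** In Protocol 5.2.3, separate the end of study procedures from the end of data collection for patients already ablated. The investigator keeps the ability to stop further study procedures for safety, but that decision does not end follow-up. Adverse events, vital status and, where feasible, the rhythm monitoring already scheduled continue to month 12 unless the patient withdraws consent for data collection.

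State in Protocol 6.1 and 6.7 and in SAP 4.1.2 and 6.3 that data collected this way count in the Safety population and, for rhythm outcomes, in the mITT analysis. This extends the principle that 5.3.8 already applies after a third ablation.

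The cost is a sentence or two in each document, consent wording, and a few already-planned visits or contacts for a small number of patients. The sample size stays at 292 evaluable and 374 enrolled.

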#### 5.2.4 – Expected total duration of the clinical investigation

The clinical investigation will not begin in any center until:

- Approval has been obtained from the relevant Ethics Committees or IRB, including approval from national and/or local Ethics Committees or IRBs as required by current national and/or local laws on the rights, safety, and welfare of human subjects.
- Approval or no objection has been obtained from regulatory Health Authorities, as required by current national and/or local laws on the rights, safety, and welfare of human subjects.
- Liability coverage has been obtained by the sponsor, as required by current national and/or local laws on the rights, safety, and welfare of human subjects.
- Investigator agreement has been obtained from the investigator(s) in the center, as required by the Declaration of Helsinki and national/local laws on the rights, safety, and welfare of human subjects.

The expected total duration of the study is 41 months:

*This document is confidential and proprietary of Volta Medical. All copy is considered uncontrolled. User must verify the revision of uncontrolled copy before use.*

	CLIP-01-002-E	CONFIDENTIAL
	CLINICAL INVESTIGATION PLAN	F 09 XX 01 Rev.A Page 20/47

- 4-month set-up
- 22-month enrollment
- 12-month follow-up
- 3-month database lock, analysis, and close-out

